10.8 Appendix 8: List of Potential Immune-Mediated Diseases

The GSK list of pIMDs is based on MedDRA version 26.1.

Table 16 GSK List of pIMD MedDRA Terms

MedDRA Term Name	Term Level
Acute cutaneous lupus erythematosus	PT
Acute disseminated encephalomyelitis	PT
Acute febrile neutrophilic dermatosis	PT
Acute flaccid myelitis	PT
Acute haemorrhagic leukoencephalitis	PT
Acute haemorrhagic oedema of infancy	PT
Acute macular neuroretinopathy	PT
Acute motor axonal neuropathy	PT
Acute motor-sensory axonal neuropathy	PT
Acute necrotising myelitis	PT
Addison's disease	PT
Administration site vasculitis	PT
AGEP-DRESS overlap	PT
Alopecia areata	PT
Alveolar proteinosis	PT
Ankylosing spondylitis	PT
Antibody-dependent enhancement	PT
Anti-glomerular basement membrane disease	PT
Anti-LRP2 nephropathy	PT
Anti-myelin-associated glycoprotein associated polyneuropathy	PT
Anti-neutrophil cytoplasmic antibody positive vasculitis	PT
Antiphospholipid syndrome	PT
Anti-RNA polymerase III antibody increased	PT
Anti-RNA polymerase III antibody positive	PT
Antisynthetase syndrome	PT
Aortitis	PT
Application site vasculitis	PT
Arteritis	PT
Arteritis coronary	PT

MedDRA Term Name	Term Level
Arthritis enteropathic	PT
Arthritis reactive	PT
ASIA syndrome	PT
Atrophic thyroiditis	PT
Autoimmune anaemia	PT
Autoimmune aplastic anaemia	PT
Autoimmune arthritis	PT
Autoimmune blistering disease	PT
Autoimmune cerebellar ataxia	PT
Autoimmune cholangitis	PT
Autoimmune colitis	PT
Autoimmune demyelinating disease	PT
Autoimmune dermatitis	PT
Autoimmune disorder	PT
Autoimmune encephalopathy	PT
Autoimmune endocrine disorder	PT
Autoimmune enteropathy	PT
Autoimmune eye disorder	PT
Autoimmune haemolytic anaemia	PT
Autoimmune heparin-induced thrombocytopenia	PT
Autoimmune hepatitis	PT
Autoimmune hyperlipidaemia	PT
Autoimmune hypothyroidism	PT
Autoimmune inner ear disease	PT
Autoimmune lung disease	PT
Autoimmune lymphoproliferative syndrome	PT
Autoimmune myocarditis	PT
Autoimmune myositis	PT
Autoimmune nephritis	PT
Autoimmune neuropathy	PT
Autoimmune neutropenia	PT
Autoimmune pancreatitis	PT
Autoimmune pancytopenia	PT

MedDRA Term Name	Term Level
Autoimmune pericarditis	PT
Autoimmune retinopathy	PT
Autoimmune thyroid disorder	PT
Autoimmune thyroiditis	PT
Autoimmune uveitis	PT
Autoinflammatory disease	PT
Axial spondyloarthritis	PT
Axonal and demyelinating polyneuropathy	PT
Axonal neuropathy	PT
Behcet's syndrome	PT
Bell's palsy	PT
Bickerstaff's encephalitis	PT
Birdshot chorioretinopathy	PT
Brachial plexopathy	PT
Bulbar palsy	PT
C1q nephropathy	PT
CANOMAD syndrome	PT
Capillaritis	PT
Capillary leak syndrome	PT
Caplan's syndrome	PT
Cardiac sarcoidosis	PT
Central nervous system lupus	PT
Central nervous system vasculitis	PT
Cerebral arteritis	PT
Cholangitis sclerosing	PT
Chronic autoimmune glomerulonephritis	PT
Chronic cutaneous lupus erythematosus	PT
Chronic inflammatory demyelinating polyradiculoneuropathy	PT
Chronic lymphocytic inflammation with pontine perivascular enhancement responsive to steroids	PT
Chronic pigmented purpura	PT
Clinically isolated syndrome	PT
Coeliac disease	PT

MedDRA Term Name	Term Level
Cogan's syndrome	PT
Cold type haemolytic anaemia	PT
Colitis erosive	PT
Colitis microscopic	PT
Colitis ulcerative	PT
Collagen-vascular disease	PT
Concentric sclerosis	PT
Coombs positive haemolytic anaemia	PT
Cranial nerve disorder	PT
Cranial nerve palsies multiple	PT
Cranial nerve paralysis	PT
CREST syndrome	PT
Crohn's disease	PT
Cutaneous lupus erythematosus	PT
Cutaneous sarcoidosis	PT
Cutaneous vasculitis	PT
Demyelinating polyneuropathy	PT
Demyelination	PT
Dermatitis bullous	PT
Dermatitis herpetiformis	PT
Dermatomyositis	PT
Diffuse vasculitis	PT
Encephalitis allergic	PT
Encephalitis autoimmune	PT
Encephalitis brain stem	PT
Encephalitis haemorrhagic	PT
Encephalitis periaxialis diffusa	PT
Encephalitis post immunisation	PT
Encephalitis toxic	PT
Encephalomyelitis	PT
Endocrine ophthalmopathy	PT
Enhanced respiratory disease	PT
Enteropathic spondylitis	PT

MedDRA Term Name	Term Level
Eosinophilic fasciitis	PT
Eosinophilic granulomatosis with polyangiitis	PT
Erythema induratum	PT
Erythema multiforme	PT
Erythema nodosum	PT
Evans syndrome	PT
Expanded disability status scale score decreased	PT
Expanded disability status scale score increased	PT
Facial paralysis	PT
Facial paresis	PT
Felty's syndrome	PT
Fibrillary glomerulonephritis	PT
Fulminant type 1 diabetes mellitus	PT
Giant cell arteritis	PT
Giant cell myocarditis	PT
Glomerulonephritis membranoproliferative	PT
Glomerulonephritis membranous	PT
Glomerulonephritis rapidly progressive	PT
Glossopharyngeal nerve paralysis	PT
Goodpasture's syndrome	PT
Gout	PT
Gouty arthritis	PT
Gouty tophus	PT
Granulomatosis with polyangiitis	PT
Granulomatous dermatitis	PT
Graves' disease	PT
Guillain-Barre syndrome	PT
Haemorrhagic occlusive retinal vasculitis	PT
Haemorrhagic vasculitis	PT
Hashimoto's encephalopathy	PT
Hashitoxicosis	PT
Henoch-Schonlein purpura	PT
Henoch-Schonlein purpura nephritis	PT

MedDRA Term Name	Term Level
Hypersensitivity vasculitis	PT
Hypoglossal nerve paralysis	PT
Hypoglossal nerve paresis	PT
Idiopathic inflammatory myopathy	PT
Idiopathic interstitial pneumonia	PT
Idiopathic pulmonary fibrosis	PT
IgA nephropathy	PT
IgM nephropathy	PT
IIIrd nerve paralysis	PT
IIIrd nerve paresis	PT
Immune effector cell-associated HLH-like syndrome	PT
Immune thrombocytopenia	PT
Immune-complex membranoproliferative glomerulonephritis	PT
Immune-mediated adrenal insufficiency	PT
Immune-mediated adverse reaction	PT
Immune-mediated arthritis	PT
Immune-mediated cholangitis	PT
Immune-mediated cholestasis	PT
Immune-mediated cystitis	PT
Immune-mediated cytopenia	PT
Immune-mediated dermatitis	PT
Immune-mediated encephalitis	PT
Immune-mediated encephalopathy	PT
Immune-mediated endocrinopathy	PT
Immune-mediated enterocolitis	PT
Immune-mediated gastritis	PT
Immune-mediated hepatic disorder	PT
Immune-mediated hepatitis	PT
Immune-mediated hyperthyroidism	PT
Immune-mediated hypophysitis	PT
Immune-mediated hypothyroidism	PT
Immune-mediated lung disease	PT
Immune-mediated myasthenia gravis	PT

MedDRA Term Name	Term Level
Immune-mediated myelitis	PT
Immune-mediated myocarditis	PT
Immune-mediated myositis	PT
Immune-mediated nephritis	PT
Immune-mediated neurological disorder	PT
Immune-mediated neuropathy	PT
Immune-mediated oesophagitis	PT
Immune-mediated optic neuritis	PT
Immune-mediated pancreatitis	PT
Immune-mediated pancytopenia	PT
Immune-mediated pericarditis	PT
Immune-mediated polyserositis	PT
Immune-mediated renal disorder	PT
Immune-mediated scleritis	PT
Immune-mediated thyroiditis	PT
Immune-mediated uveitis	PT
Immune-mediated vasculitis	PT
Immunoglobulin G4 related disease	PT
Inclusion body myositis	PT
Inflammatory bowel disease	PT
Injection site vasculitis	PT
Insulin autoimmune syndrome	PT
Interstitial granulomatous dermatitis	PT
Interstitial lung disease	PT
Intramyelinic oedema	PT
IVth nerve paralysis	PT
IVth nerve paresis	PT
Juvenile idiopathic arthritis	PT
Juvenile polymyositis	PT
Juvenile psoriatic arthritis	PT
Juvenile spondyloarthritis	PT
Kawasaki's disease	PT
Keratoderma blenorrhagica	PT

MedDRA Term Name	Term Level
Langerhans' cell histiocytosis	PT
Laryngeal rheumatoid arthritis	PT
Latent autoimmune diabetes in adults	PT
Leukoencephalomyelitis	PT
Leukoencephalopathy	PT
Lewis-Sumner syndrome	PT
Lichen planopilaris	PT
Lichen planus	PT
Lichen planus pemphigoides	PT
Linear IgA disease	PT
Liver sarcoidosis	PT
Loefgren syndrome	PT
Lumbosacral radiculoplexus neuropathy	PT
Lupoid hepatic cirrhosis	PT
Lupus anticoagulant hypoprothrombinaemia syndrome	PT
Lupus cystitis	PT
Lupus encephalitis	PT
Lupus endocarditis	PT
Lupus enteritis	PT
Lupus hepatitis	PT
Lupus myocarditis	PT
Lupus myositis	PT
Lupus nephritis	PT
Lupus pancreatitis	PT
Lupus pleurisy	PT
Lupus pneumonitis	PT
Lupus vasculitis	PT
Lupus-like syndrome	PT
Lymphocytic hypophysitis	PT
MAGIC syndrome	PT
Marburg's variant multiple sclerosis	PT
Marine Lenhart syndrome	PT
Melkersson-Rosenthal syndrome	PT

MedDRA Term Name	Term Level
Membranous-like glomerulopathy with masked IgG-kappa deposits	PT
Mesangioproliferative glomerulonephritis	PT
Metastatic cutaneous Crohn's disease	PT
Microscopic enteritis	PT
Microscopic polyangiitis	PT
Miller Fisher syndrome	PT
Mixed connective tissue disease	PT
Mononeuritis	PT
Mononeuropathy multiplex	PT
Morphea	PT
Morvan syndrome	PT
Mucous membrane pemphigoid	PT
Multifocal motor neuropathy	PT
Multiple sclerosis	PT
Multiple sclerosis pseudo relapse	PT
Multiple sclerosis relapse	PT
Multiple sclerosis relapse prophylaxis	PT
Multisystem inflammatory syndrome	PT
Multisystem inflammatory syndrome in adults	PT
Multisystem inflammatory syndrome in children	PT
Muscular sarcoidosis	PT
Myasthenia gravis	PT
Myasthenia gravis crisis	PT
Myasthenic syndrome	PT
Myelin oligodendrocyte glycoprotein antibody-associated disease	PT
Myelitis	PT
Myelitis transverse	PT
Myocarditis	PT
Myopericarditis	PT
Narcolepsy	PT
Neuralgic amyotrophy	PT
Neuritis	PT
Neuritis cranial	PT

MedDRA Term Name	Term Level
Neuromyelitis optica pseudo relapse	PT
Neuromyelitis optica spectrum disorder	PT
Neuropsychiatric lupus	PT
Neurosarcoidosis	PT
Nodular vasculitis	PT
Noninfectious myelitis	PT
Noninfective encephalitis	PT
Noninfective encephalomyelitis	PT
Noninfective ophoritis	PT
Ocular myasthenia	PT
Ocular pemphigoid	PT
Ocular sarcoidosis	PT
Ocular vasculitis	PT
Oculofacial paralysis	PT
Olfactory nerve disorder	PT
Optic ischaemic neuropathy	PT
Optic neuritis	PT
Optic neuropathy	PT
Optic perineuritis	PT
Orexin deficiency	PT
Overlap syndrome	PT
Palindromic rheumatism	PT
Palisaded neutrophilic granulomatous dermatitis	PT
Palpable purpura	PT
Panencephalitis	PT
Paresis cranial nerve	PT
Pemphigoid	PT
Pemphigus	PT
Pericarditis	PT
Pericarditis lupus	PT
Pericarditis rheumatic	PT
Peripheral spondyloarthritis	PT
Peritonitis lupus	PT

MedDRA Term Name	Term Level
Pernicious anaemia	PT
Pleuroparenchymal fibroelastosis	PT
Polyarteritis nodosa	PT
Polychondritis	PT
Polyglandular autoimmune syndrome type I	PT
Polyglandular autoimmune syndrome type II	PT
Polyglandular autoimmune syndrome type III	PT
Polymyalgia rheumatica	PT
Polymyositis	PT
Polyneuropathy idiopathic progressive	PT
Primary biliary cholangitis	PT
Primary progressive multiple sclerosis	PT
Proctitis ulcerative	PT
Progressive facial hemiatrophy	PT
Progressive multiple sclerosis	PT
Progressive relapsing multiple sclerosis	PT
Psoriasis	PT
Psoriatic arthropathy	PT
Pulmonary fibrosis	PT
Pulmonary renal syndrome	PT
Pulmonary sarcoidosis	PT
Pulmonary vasculitis	PT
Pyoderma gangrenosum	PT
Pyostomatitis vegetans	PT
Radiculitis brachial	PT
Radiologically isolated syndrome	PT
Rasmussen encephalitis	PT
Raynaud's phenomenon	PT
Relapsing multiple sclerosis	PT
Relapsing-remitting multiple sclerosis	PT
Renal arteritis	PT
Renal vasculitis	PT
Retinal occlusive vasculitis	PT

MedDRA Term Name	Term Level
Retinal vasculitis	PT
Reynold's syndrome	PT
Rheumatic brain disease	PT
Rheumatic disorder	PT
Rheumatoid arthritis	PT
Rheumatoid arthritis-associated interstitial lung disease	PT
Rheumatoid bursitis	PT
Rheumatoid lung	PT
Rheumatoid meningitis	PT
Rheumatoid neutrophilic dermatosis	PT
Rheumatoid nodule	PT
Rheumatoid pleuritis	PT
Rheumatoid scleritis	PT
Rheumatoid vasculitis	PT
Rhupus syndrome	PT
Sarcoidosis	PT
Sarcoidosis of lymph node	PT
Satoyoshi syndrome	PT
Sclerodactylia	PT
Scleroderma	PT
Scleroderma associated digital ulcer	PT
Scleroderma renal crisis	PT
Secondary progressive multiple sclerosis	PT
Segmented hyalinising vasculitis	PT
Shrinking lung syndrome	PT
Silent thyroiditis	PT
Sjogren's syndrome	PT
SJS-TEN overlap	PT
SLE arthritis	PT
Spondylitis	PT
Spondyloarthropathy	PT
Stevens-Johnson syndrome	PT
Still's disease	PT

MedDRA Term Name	Term Level
Stoma site vasculitis	PT
Subacute cutaneous lupus erythematosus	PT
Subacute inflammatory demyelinating polyneuropathy	PT
Susac's syndrome	PT
Sympathetic ophthalmia	PT
Systemic lupus erythematosus	PT
Systemic lupus erythematosus disease activity index abnormal	PT
Systemic lupus erythematosus disease activity index decreased	PT
Systemic lupus erythematosus disease activity index increased	PT
Systemic lupus erythematosus rash	PT
Systemic scleroderma	PT
Systemic sclerosis pulmonary	PT
Takayasu's arteritis	PT
Terminal ileitis	PT
Testicular autoimmunity	PT
Thromboangiitis obliterans	PT
Thrombocytopenic purpura	PT
Thrombosis with thrombocytopenia syndrome	PT
Thrombotic thrombocytopenic purpura	PT
Tongue paralysis	PT
Toxic epidermal necrolysis	PT
Trigeminal nerve paresis	PT
Trigeminal palsy	PT
Tubulointerstitial nephritis and uveitis syndrome	PT
Tumefactive multiple sclerosis	PT
Type 1 diabetes mellitus	PT
Uhthoff's phenomenon	PT
Ulcerative keratitis	PT
Undifferentiated connective tissue disease	PT
Undifferentiated spondyloarthritis	PT
Urticarial vasculitis	PT
Uveitis	PT
Vaccination site vasculitis	PT

MedDRA Term Name	Term Level
Vagus nerve paralysis	PT
Vascular purpura	PT
Vasculitic rash	PT
Vasculitic ulcer	PT
Vasculitis	PT
Vasculitis gastrointestinal	PT
Vasculitis necrotising	PT
VIth nerve paralysis	PT
VIth nerve paresis	PT
Vitiligo	PT
Vocal cord paralysis	PT
Vocal cord paresis	PT
Vogt-Koyanagi-Harada disease	PT
Warm autoimmune haemolytic anaemia	PT
XIth nerve paralysis	PT

Abbreviations: LLT=lowest level term; PT=preferred term.

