8.5.5 Regulatory Reporting Requirements for SAEs and Other Events

Prompt notification by the investigator to the Sponsor of an SAE or pIMD is essential so that legal obligations and ethical responsibilities toward the safety of participants and the safety of a study intervention under clinical investigation are met.

The Sponsor has a legal responsibility to notify both the local regulatory authority and other regulatory agencies about the safety of a study intervention under clinical investigation. The Sponsor will comply with country-specific regulatory requirements relating to safety reporting to the regulatory authority, IRBs/IECs, and investigators.

For SAEs and pIMDs, the investigator must always provide an assessment of causality at the time of the initial report, as defined in the Section 10.5.3.

An investigator who receives an investigator safety report describing an SAE or other specific safety information (e.g., summary or listing of SAEs) from the Sponsor will review and then file it along with the IB and will notify the IRB/IEC, if appropriate according to local requirements.

Table 8 Timeframes for Submitting SAE, Pregnancy, pIMDs to IQVIA

Type of event	Initial reports		Follow-up of relevant information on a previous report	
	Timeframe	Documents	Timeframe	Documents
SAEs	24 hours* ‡‡	Electronic [‡] AEs Report	24 hours*	Electronic [‡] AEs Report
Pregnancies	24 hours*	Electronic pregnancy report	24 hours *	Electronic pregnancy report
pIMDs (whether serious or non-serious)	24 hours** ‡‡	Electronic [‡] AEs Report	24 hours*	Electronic [‡] AEs Report

Abbreviation: AE=adverse event; SAE=serious adverse event; pIMD=potential immune-mediated disease.

* Timeframe allowed after receipt or awareness of the information by the investigator/site staff.

**Timeframe allowed once the investigator determines that the event meets the protocol definition of a pIMD.

[‡] Paper AEs report may be submitted in the case that the electronic system is not functioning. The paper report will be dated and signed by the investigator (or designee). For each SAE/pIMD, the investigator(s) must document in the medical notes that they have reviewed the SAE/pIMD and have provided an assessment of causality.

‡‡ The investigator will be required to confirm review of the SAE/pIMD causality by ticking the ‘reviewed’ box in the electronic Expedited Adverse Events Report within 72 hours of submission of the SAE/pIMD.

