8.5.7 Adverse Events of Special Interest

8.5.7.1 Potential Immune-Mediated Diseases

Potential immune-mediated diseases are a subset of AESIs that include autoimmune diseases and other inflammatory and/or neurologic disorders of interest which may or may not have an autoimmune etiology. Adverse events that need to be recorded and reported as pIMDs include those listed in [Table 16](#) and must be reported in an expedited manner regardless of causality, seriousness, or medical opinion on etiology.

The investigator(s) must exercise their medical/scientific judgment to determine whether other diseases have an autoimmune origin (i.e., pathophysiology involving systemic or organ-specific pathogenic autoantibodies) and should also be recorded as a pIMD. In addition, the investigator should categorize each pIMD as a new onset condition (if it started following vaccination) in the eCRF.

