10.9 Appendix 9: Protocol and Amendment History

The Protocol Amendment Summary of Changes Table for the current amendment is located directly before the table of contents.

Amendment 1.0: 23 June 2023

Overall Rationale for the Amendment 1.0:

This protocol has been amended to extend the collection of medically attended adverse events (MAEs) and to include a 30-minute observation period after each vaccination as required by the US Food and Drug Administration (FDA).

Added text in ***bold italic***, deleted text in ~~strikethrough~~.

Section # and Name	Description of Change from Original Protocol to Amendment 1.0	Brief Rationale
1.1 Synopsis, 1.2 Study Design, 1.3 Schedule of Activities, 3.0 Objectives and Endpoints, 8.5.1 Time Period and Frequency for Collecting AE, SAE, pIMD Information, 9.4.3.2 Safety, 9.5.1.1 Interim Analysis at Day 43, 9.5.1.2 Final Analysis (6 Months Post Dose 2)	Extended collection of MAEs to Visit 6/EOS (6 months post dose 2)	FDA requirement
1.3 Schedule of Activities	
Added Time Point task to Table 1: 30-minute observation period after each vaccine administration.
 
Deleted collection of diary card at Visit 6/EOS
	
FDA requirement
 
Diary cards are returned at Visit 5 (Day 43)

8.3.6 Post-Vaccination Observation Period	Section added	FDA requirement
8.5.2 Method of Detecting AEs and SAEs	
Added text:
 
Participants must be made aware of the requirement to report any new medical condition or worsening of any pre-existing medical condition requiring contact with a healthcare professional to the site staff.
	FDA requirement

Section # and Name	Description of Change from Original Protocol to Amendment 1.0	Brief Rationale
Global document update	Version control including version number and summary of changes were added to this document and minor edits have been made for clarity.	Version control, minor clarifications

Amendment 2.0: 22 August 2023**Overall Rationale for the Amendment 2.0:**

This protocol has been amended to replace the table titled 'List of potential Immune-Mediated Diseases (pIMDs)' with an entire listing of pIMD terms, based on the GSK MedDRA query listing, as requested by the US Food and Drug Administration (FDA).

Added text in ***bold italic***, deleted text in ~~strikethrough~~.

Section # and Name	Description of Changes from Amendment 1.0 to Amendment 2.0	Brief Rationale

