## 16.1. Adverse Events

Adverse Events (AEs) will be coded using MedDRA central coding dictionary, version 25.1 or higher. Adverse events will be described using frequency and percentage.

Adverse Events will be grouped by SOC, HLT and PT and summarized by study intervention at time of onset of the AE. The summary tables will present the number and percentage of total participants and number of events, by SOC and by PT for each study intervention.

For the summaries of AEs, participants who experience the same AE (in terms of the MedDRA SOC, HLT and PT) more than once will only be counted once for that event in the number of participants but all occurrences of the same event will be counted in the number of events.

Causality, as indicated by the Investigator is classed as “related” and “not related” to Q-Pan H5N8 vaccine. A “related” AE is defined as an AE with a relationship to study intervention. If a participant reports the same AE more than once within that SOC / PT, the AE with the worst-case relationship to study intervention will be used in the corresponding relationship summaries for each study intervention.

See [APPENDIX 2](#) for handling of partial dates for AEs.

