#### **16.1.5. pIMDs**

pIMDs will be summarized and listed as follows:

- The number and percentage of participants, with exact 95% CIs, with at least one report of pIMDs (all pIMDs, causally related) with onset after each vaccination administration up to Day 43 and up to study end (i.e., 6 months post-last vaccination) will be summarized.
- All pIMDs will also be described in detail in a tabular listing. Classification by new onset vs exacerbations of pIMDs will also be presented.

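### SAP 16.1.5 counts reported pIMDs without matching coded AEs to the protocol's Table 16 terms, so a listed event that a site did not flag could be missing from a primary safety endpoint

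*Protocol*

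**What the plan says.** **Endpoint.** Protocol 3.0 and SAP 2.1 list pIMD occurrence, to Day 43 and to 6 months after dose 2, among the primary safety endpoints. The SAP 2.4 estimand row assigns it to the Exposed Set and gives no rule for identifying a pIMD.

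**Definition for sites.** Protocol 8.5.7.1 says "Adverse events that need to be recorded and reported as pIMDs include those listed in" Table 16, and that these "must be reported in an expedited manner regardless of causality, seriousness, or medical opinion on etiology". It adds a second route for diseases not on the list: "The investigator(s) must exercise their medical/scientific judgment to determine whether other diseases have an autoimmune origin".

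**The list.** Appendix 8 states "The GSK list of pIMDs is based on MedDRA version 26.1", and every entry in Table 16 is at PT level. The Amendment 2.0 rationale in Appendix 9 explains its origin: the former table was replaced "with an entire listing of pIMD terms, based on the GSK MedDRA query listing".

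**Who decides in practice.** A footnote to Table 8 (Protocol 8.5.5) starts the reporting clock for a pIMD as follows: "Timeframe allowed once the investigator determines that the event meets the protocol definition of a pIMD".

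**Analysis.** SAP 16.1.5 summarises participants "with at least one report of pIMDs (all pIMDs, causally related) with onset after each vaccination administration up to Day 43". It repeats the summary for the whole follow-up period, and also presents new onset against exacerbation. SAP 16.1 says AEs "will be coded using MedDRA central coding dictionary, version 25.1 or higher". The supplied SAP text does not cite Table 16 or Appendix 8.

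**The concern.** For a listed disease the protocol leaves the site no discretion. But the list is written in a vocabulary that the site does not use when it records an event. The investigator enters a verbatim term and a coder assigns the PT later (Protocol 9.4.3.2; SAP 16.1.2). A PT list can be applied completely and uniformly only to coded data, and the SAP has no step that does so.

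The natural reading of SAP 16.1.5 is that the site's flag determines the count. Table 16 includes terms such as gout, psoriasis, lichen planus, facial paresis and spondylitis, which a site could plausibly enter as ordinary AEs. An event of that kind would be one the protocol requires to be reported as a pIMD, yet it could be absent from the table meant to show pIMDs. Because 16.1.5 states no rule, two programmers could also build the endpoint differently: flag only, PT match only, or both.

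**Working it through.** No pIMD rate is stated in the plan, so there is no figure to reproduce. The check is mainly textual, with one calculation for scale.

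**1. Trace a recorded AE through both documents.** Inputs are Protocol 8.5.7.1 (what must be reported as a pIMD) and SAP 16.1.5 read naturally (a pIMD is what the site reported as one).

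| Recorded event | To be reported as a pIMD under 8.5.7.1 | Counted in 16.1.5 |
|---|---|---|
| PT in Table 16, flagged | Yes | Yes |
| PT not listed, judged autoimmune, flagged | Yes | Yes |
| PT in Table 16, not flagged | Yes | No |
| PT not listed, not flagged | No, unless it should have been judged autoimmune | No |

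The two documents part in the third row. A PT match alone would lose the second row, so neither source is sufficient by itself and the rule has to be their union.

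**2. Where a third-row event would still be seen.** Protocol 8.5.1 collects unsolicited AEs for 21 days after each dose, MAEs throughout, and SAEs to 6 months. The event would appear in those outputs if it met their criteria and windows. It would be missing from the pIMD endpoint, not from the database.

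**3. Compare with a term selection the SAP does specify.** SAP 16.1.3 gives Table H, a list of MedDRA lower-level-term codes used to select AEs for a registry-posting summary. That summary has a reproducible term rule, and the primary pIMD endpoint has none.

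**4. Coding version.** The list is tied to 26.1. The SAP sets 25.1 as a floor, which allows 26.1 but does not require it. No version is fixed for matching the list.

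**5. Scale.** Inputs are the planned n = 65 per age-by-dose subgroup (Protocol 9.2; SAP 2.5), assuming all 65 are in the Exposed Set, and the exact Clopper-Pearson 95% interval. Analyses are reported separately by age group (SAP 6), so 65 is the relevant denominator.

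- x = 0: upper limit = 1 − 0.025^(1/65) = 5.52%. Result 0% (0 to 5.5%).
- x = 1: estimate = 1/65 = 1.54%; lower limit = 1 − 0.975^(1/65) = 0.039%; upper limit = 0.975 quantile of Beta(2, 64) = 8.28%. Result 1.5% (0.04 to 8.3%).
- Difference in upper limits: 8.28 − 5.52 = 2.76 percentage points.

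These figures show what one event is worth in a subgroup. They do not estimate how many events would be missed.

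**The case against.** The best defence is that the SAP is silent, not restrictive. It does not say that only flagged events count, and it does not rule out a term match. SAP 16.1.4 uses the same reporting phrase for SAEs, so the wording may be stock. Output detail is left to templates and mock shells (SAP 4.3 and 8) that are not in the supplied text. Sites must report every listed term, so an unflagged one would be a site deviation. The Table 8 footnote governs a reporting clock, not entry to the analysis. A physician reviews unsolicited verbatims (SAP 16.1.2) and the SRT monitors cumulative blinded safety data (SAP 4.1).

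Much of this stands. It makes the omission a risk rather than a certainty. It does not remove the risk: none of these safeguards is described as a comparison with Table 16, and a primary endpoint should not depend on an unstated derivation.

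Four stronger readings are tempting, and the documents do not support them:

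- A reader might infer a dictionary conflict, but 25.1 or higher permits 26.1.
- A reader might infer from the 26.0 to 26.1 update in Amendment 3.0 that sites worked from materially different lists. The documents do not show that any term differs between the two.
- A reader might treat Table 16 as the whole definition, but 8.5.7.1 makes it non-exhaustive.
- A reader might conclude that the pIMD rate is undercounted. The documents give no expected number of pIMDs and no rate of missed flags.

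**Conclusion.** The point holds as a gap in how a primary safety endpoint is derived. SAP 16.1.5 does not apply the protocol's PT list to coded AEs, and on its natural reading a recorded, listed but unflagged event would not be counted as a pIMD. Any resulting error would lower the reported percentage, but its size cannot be computed from the documents. One event in a subgroup of 65 is worth 1.5 percentage points and about 2.8 points on the upper confidence limit.

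This rests on three assumptions: that the reported pIMD in 16.1.5 means the site's flag, that the mock shells add no term match, and that the planned subgroup size is achieved. No hypothesis test is affected, since the safety analyses are descriptive, and nothing here shows a difference between dose groups. It is a cheap improvement worth making, not a proven bias.

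**What to change.** Amend SAP 16.1.5 as follows:

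- Define a pIMD as any event flagged by the investigator, including an unlisted disease judged autoimmune, **or** any recorded AE whose coded PT is in Table 16.
- Name one MedDRA version for both the AE coding and the list used in the match.
- Before each lock, query every unflagged match with the site, including whether it is new onset or an exacerbation. The investigator enters the onset category for events recorded as pIMDs, so unflagged matches would otherwise lack it.
- Show the investigator-flagged count beside the union, so the effect of the match is visible.

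The cost is one programmed comparison on data already collected, a few site queries per lock, and a short change of wording. The match needs no treatment codes. Some matches will prove to be pre-existing conditions. The match also has a limit: after the 21-day windows, an event that is neither serious nor medically attended, and that the site did not recognise as a pIMD, may never have been recorded. No term match can recover it.
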